### 2.2 BACKGROUND

The brain is hypothesized to rest near a critical point and divergence from this critical point is increasingly regarded as an important biomarker for psychopathology and neuropathy (O’Byrne et al., 2022). Importantly, the brain enters a state of sub-critical dynamics when people engage in tasks versus rest (Pfeffer et al. 2018) and becomes even more sub-critical with increasing task demands (Churchill et al., 2016; Kardan et al., 2020). We thus hypothesize that phenomenological, subjective cognitive effort indexes divergence from criticality associated with demanding task engagement. Given that deficient cognitive effort is a core feature of multiple forms of psychopathology (Patzelt et al. 2019, [name] and Braver, 2015), it is essential to understand the mechanisms of subjective effort sensitivity. If, as we hypothesize, subjective effort reflects divergence from criticality, we may one day be able to predict subjective effort by measuring a brain’s proximity to a critical point, and develop treatments for targeting the mechanisms which underlie divergence from criticality in some individuals.

A key control parameter thought to regulate proximity to criticality is the balance of cortical excitation to inhibition or “E/I balance” (Pfeffer et al. 2018; Agrawal et al. 2018). Prior work has shown that atomoxetine, a norepinephrine reuptake inhibitor, can modulate brain dynamics making them less sub-critical and more closely approximate critical dynamics, even when people are engaged in a task versus rest, consistent with the hypothesis that norepinephrine increases cortical E/I balance (Pfeffer et al. 2018).

Transcranial magnetic stimulation (TMS) is another promising tool for modulating cortical E/I balance and may thereby impact on brain criticality. Specifically, theta-burst stimulation (TBS) protocols have been shown to alternately increase (using intermittent TBS) or decrease (continuous TBS) cortical E/I balance (Desforges et al. 2022; Huang et al. 2005; Chung et al. 2018). TMS is widely used for treatment of depression (Cole et al., 2022), yet the mechanisms of action are unclear. It is therefore tempting to speculate that modulation of E/I balance and critical dynamics contribute to treatment efficacy – especially given that deficient cognitive effort is a core feature of depression ([name] et al. 2022). TMS is also an attractive experimental tool by virtue of its capacity to precisely target cortical regions. Since oculomotor control is mediated by the frontal eye fields and performance can be disrupted by TMS stimulation there (Mackey and Curtis, 2017), it is reasonable to posit that modulation of E/I balance and cortical dynamics in the frontal eye fields might mediate oculomotor control and the subjective effort associated with performing such tasks.

Recent studies have demonstrated that it is possible to estimate a functional E/I balance measure from EEG data, based on several minutes of resting EEG data (Bruining et al. 2021). In principle, we should thus be able to estimate the consequences of TBS on cortical excitability more directly, through intrinsic functional dynamics.

## 2.3 RISK/BENEFIT ASSESSMENT

### 2.3.1 KNOWN POTENTIAL RISKS

#### Information Risks

The potential for loss of electronic and paper records of personal information used for screening may place the participant at low risk for loss of privacy. The magnitude of this risk is also low as information about an individual participant’s behavioral performance on abstract cognitive control tasks and / or their dynamic brain response to task engagement or TMS is of minimal use outside of the context of this experiment.

#### Physical Risks or Harms

### EEG

EEG Devices are categorized as NSR by FDA (<https://www.fda.gov/media/75459/download>).

### MRI

The use of the legally marketed MRI system in research mode will be performed under operating conditions below each of the limits (field strength, Specific Absorption Rate, time rate of change of gradient fields and sound pressure levels) deemed to be significant risk by the FDA as stated in the FDA guidance document, Criteria for Significant Risk Investigations of Magnetic Resonance Diagnostic Devices. (<https://www.fda.gov/media/71385/download>).

There are no known significant risks associated with participation in MRI at the levels of magnetic field proposed here, beyond those due to the effect of a magnetic field on an implanted metal fragment or medical device.

### TMS

#### Overview:

Participating in a TMS study provides indirect benefit to the participants in terms of outstanding scientific knowledge gained about brain function, but it is low risk given that the stimulation parameters being used are within the established safety norms (Rossi et al. 2009; 2020) and we will only enroll healthy participants without contraindication for TMS. In what follows, we detail the specific risks associated with this protocol and the steps we will take to protect against risk beyond those already described in relation to the consent process.

#### Risks associated with participation in TMS experiments:

(1) Heating, induced voltages, and magnetic field effects. The action of the magnetic field on any implanted or worn metal in, on, or around the head poses a significant risk. Magnetic fields can move or dislodge metal, induce current in conductive metals, cause heating around metal components, and/or affect the operation of any metal device. Thus, it is crucial to screen participants for any irremovable metal in or around the head. Our health screening includes the relevant screening questions.

(2) Hearing changes. Movement of the TMS coil within its casing when current is passed through it produces an audible “click”. Though this click is often not perceived as loud due to the stapedial reflex, it can nevertheless reach 140 dB or more of sound pressure. This exceeds OSHA sound level limits and could produce changes in hearing levels if exposed repeatedly. Thus, we will require all participants to wear earplugs. In addition, we will exclude participants with potential hearing problems.

(3) Induced seizure: Though exceedingly rare even in patients with epilepsy, induction of a “generalized” seizure is the most severe adverse event associated with TMS. A seizure is an episode of excessive brain activity and stiff muscle activity (often referred to as a “convulsion” or “fit”). Seizure risk increases at high stimulator output intensities, at high frequencies of stimulation, with multiple repeated trains of

stimulation, with long durations of stimulation, with short inter-train-intervals, and when stimulating participants with reduced seizure thresholds. However, the risk of seizure induction is minimal to negligible if TMS parameters are kept within the prescribed consensus safety parameters (Rossi et al., 2009; Rossi et al. 2020), and participants are carefully screened for seizure risk. Indeed, over the past decade of experience in both clinical and research domains, this risk has been reduced to the order of one 1 in 89,000 cases (Rossi et al 2020).

(4) TMS application site (scalp) discomfort/headache: The stimulation itself is felt as a tapping sensation on the scalp. The tapping induced by rTMS at high stimulator output intensity can feel sharper and even painful. In addition to a tapping or percussion sensation on the head, muscles and peripheral nerves in the head and face react to TMS with sensations such as twitching of superficial muscle groups. Depending on the location of stimulation, these sensations can be more or less bothersome. The sum of these sensations can range from tolerable to irritating to mildly painful. Beyond informing participants of these risks explicitly during the consent procedures, we will also ask participants about their comfort level throughout the session, and will reduce the stimulator output intensity to their comfort level or stop the session entirely depending on the feedback they give us.

Some individuals who undergo TMS experience a headache, though this may be due to the experimental set up as much as the TMS itself. Headaches usually start after the session (20 mins to 3 hours). In the event of a participant informing us that a headache is coming on during the session, we will allow the participant to cope with the headache in their preferred way, including termination of the session if they wish.

TMS is considered low risk when protocols use stimulation parameters within established international safety norms. Parameters and procedures for all protocols cited here fall within previously published international consensus safety guidelines (Rossi et al., 2009; Rossi et al., 2020) which were incorporated into FDA's Class II Special Controls Guidance Document: Repetitive Transcranial Magnetic Stimulation (rTMS) Systems in "Table 2. Maximum Safe Train Duration (seconds) Limits for Avoiding Seizures." (<https://www.fda.gov/media/81495/download>).

(A) Single pulse TMS to primary motor cortex:

Delivery of single TMS pulses (< 1 Hz) over motor cortex will primarily be used in studies of cortical excitability. Single TMS pulses will be delivered at precisely timed points during an experimental trial to either motor cortex. When delivered over motor cortex, the elicited response in EMG of the fingers, hand, or arm will be recorded. These data can characterize changes in the excitability of motor cortex during manipulations of cognitive control due to manipulations of cognitive control or attention. The time between pulses will be irregular, as they are determined by the timings of specific trial events that may not be spaced at regular intervals. However, the minimum time between any two pulses will be 1 second to keep the frequency below 1Hz, and most will be at longer intervals (> 5 seconds).

**(B) Offline patterned repetitive TMS:**

We may apply rTMS in patterned bursts, using continuous theta-burst stimulation (cTBS) for up to 40 s offline in a single train (of 600 pulses) or, in two trains with the second train after a timed delay (for a total of 1200 pulses). On a separate session we may apply intermittent theta-burst stimulation (iTBS) for ... The pattern consists of bursts of three rapid (50 Hz) pulses delivered at a frequency of 5 Hz. In a “spaced” variant of this procedure, two trains are delivered, with a 5-15 minute break in between trains. The spaced variant is advantageous in that it produces more consistent and reliable effects on cortical E/I balance in a meta-analysis (Chung et al. 2018). Importantly, a spaced variant is deemed safe, conforming to the standards articulated in a consensus statement (Rossi et al. 2020). While spaced TBS procedures increase the overall pulse count, they do not increase stimulation intensity or frequency which are of primary concern. At present, spaced TBS procedures with higher pulse counts have been used safely in dozens of studies and hundreds of participants without incident.

Offline TBS has been shown to be effective at eliciting both disruptive and facilitative effects during tasks related to cognitive control and learning. Prior work has shown that TBS effects can last up to 60 minutes following stimulation (Opie et al., 2017; Tse et al., 2018). During this time participants will remain in the lab as the stimulation would be applied in the beginning of the experimental session. This offline technique provides a means of testing the necessity of a brain region for a given task while controlling for the potentially distracting nature of the stimulation itself. It is of higher potency and lasts for a longer duration than other forms of offline stimulation, yet it uses lower intensities and for shorter total durations of stimulation.

**(C) Paired pulse TMS**

We may apply paired pulse TMS with a pair of single pulses delivered in rapid succession to evaluate the effects of rTMS on long-interval (LICI) and short-interval cortical inhibition (SICI). To evaluate SICI, we will deliver a conditioning stimulus (CS) at 80% of participants’ resting motor threshold following rapidly by a test stimulus (TS) of that is strong enough to evoke a motor-evoked potential (MEP) of 1 mV intensity from peak-to-peak. The pair of pulses will be separated by 2 ms when evaluating SICI (Noda et al., 2017a). For LICI, both the CS and TS will be administered with the intensity required to for a 1 mV MEP, and the pulses will be separated by 100 ms (Rogasch et al., 2015). For all experimental sessions, 50-70 pairs of pulses may be delivered with 3-5 s between each pair.

---

### 2.3.2 KNOWN POTENTIAL BENEFITS

The proposed research does not guarantee direct benefits to the participants beyond the opportunity to participate in a scientific enterprise. There is a potential indirect benefit of this research as it may advance understanding of the cognitive control of sequences of tasks, knowledge that may have beneficial clinical or societal impact.

### 2.3.3 ASSESSMENT OF POTENTIAL RISKS AND BENEFITS

TMS is widely used for both clinical and experimental purposes and has garnered consensus recognition as both safe and effective for altering neuromodulation (Rossi et al. 2009; Rossi et al. 2020). Yet, TMS's effects on cortical function are poorly understood. Thus, studies like this are essential for elucidating the mechanisms by which TMS alters brain function and cognition. Additionally, correlations between critical dynamics and healthy brain functioning, and the use of criticality as a biomarker of psychopathology (O'Byrne et al. 2022), imply the need for studies of those factors which regulate critical dynamics. TMS is a safe and effective method for modulating cortical E/I balance and thus provides a valuable tool for causally testing the role of E/I balance in critical dynamics. The core value of the information to be gained in this study is therefore twofold: 1) it will test mechanistic hypotheses about how theta-burst stimulation protocols alter cortical functioning and 2) it will test hypotheses about the role E/I balance in critical dynamics with implications for oculomotor control as well as subjective cognitive effort.

To enhance the efficacy and precision of the TMS manipulation, we will collect MRI data for each participant prior to their stimulation sessions. The MRI data will provide vital information about brain morphology so that we can direct precision neuronavigation for TMS. This data is vital to ensure that we can target the cortical locations we intend with TMS so that we can make accurate inferences about their respective roles in oculomotor control and subjective effort. MRI-guided neuronavigation is also valuable because it will enable us to make precise inferences about the local effects of stimulation to sites which are commonly used in clinical TMS protocols.

As noted above, the chief risk of TMS studies is seizure, yet this risk is significantly mitigated by well established, consensus guidelines with a proven track record for safe administration (Rossi et al. 2009; Rossi et al. 2020). Key methods for minimizing seizure risk include screening against risk factors among otherwise healthy young adult participants (e.g. epilepsy, history of brain trauma, the use of anti-depressants, etc.). Additionally, we will adhere closely to safety consensus guidelines as articulated by Rossi et al., which have a proven track record of safe administration. Nevertheless, as we cannot rule out seizure risk entirely, every experiment will be run by the PI ([name]) or highly-trained staff member and a second experimenter trained to respond quickly and effectively in the event of a seizure. All experimenters will be thoroughly trained, and closely familiar with the protocol for responding including securing the participant to preclude further harm, contacting emergency medical services, remaining with and reassuring the participant until emergency medical services arrive, and subsequently documenting and reporting the incident to our IRB.

For MRI, there are no known risks beyond interactions between metal and the magnetic field. Hence, all participants are extensively screened for implanted metal. Persons at primary or secondary risk based on an implanted object or medical device will be excluded according to MRF operating procedures. Moreover, no personnel are permitted in the scanner room with any metal on their person. As such, we do not anticipate any significant risk from the application of these procedures. In rare cases, a participant

will become anxious because of lying in an enclosed space. We will exclude participants who report a history of anxiety in enclosed spaces, and we will terminate the session of a participant who expresses anxiety about lying in the bore.

All participants will be able to stop the session at any time by squeezing a ball held in one hand. The ball activates a buzzer in the control room. There is also an intercom voice link with the control room that allows verbal communication between participant and experimenters.

To minimize risks around the loss of private information, participant identifiable information will be stored separately from individual data and any screening conversations will take place in private. All electronic records will be maintained on password protected fileservers in a locked office, further protected by firewalls and other security procedures. Paper records will be maintained in locked file cabinets in locked offices.

### 3 OBJECTIVES AND ENDPOINTS

OBJECTIVES	ENDPOINTS	JUSTIFICATION FOR ENDPOINTS	PUTATIVE MECHANISMS OF ACTION
Primary			
Test whether theta-burst stimulation induces a shift towards super- (intermittent theta-burst stimulation, or iTBS) or sub-critical dynamics (continuous theta burst stimulation, or cTBS) in the cortex during rest.	Diminished markers of critical dynamics including reduced long-range temporal correlations measured by detrended fluctuation analysis, and super-critical and sub-critical avalanche branching ratios.	Long-range temporal correlations ( $< 1.0$ ) and avalanche branching dynamics are widely used metrics of distance from the critical point (degree of sub-: $< 1.0$ and super-criticality $> 1.0$ ) in EEG studies.	Long-range temporal correlations and avalanche branching ratios of 1.0 are emergent properties of dynamical systems at a critical point. By reducing and increasing the E/I balance, theta burst stimulation should make the brain more sub-critical and super-critical, respectively, thus dampening these

OBJECTIVES	ENDPOINTS	JUSTIFICATION FOR ENDPOINTS	PUTATIVE MECHANISMS OF ACTION
			emergent properties.
Test whether theta-burst stimulation to the frontal eye fields (FEF) alters cognitive control relative to sham stimulation.	Increases or decreases in accuracy in the anti-saccade task	Criticality affords the capacity for inter-regional communication in the service of, e.g., top-down control from FEF to saccade motor regions. Thus, people with brains operating closer to criticality should show greater accuracy on the anti-saccade task. If cTBS makes brains more sub-critical, they should show less anti-saccade accuracy. If iTBS makes brains more critical (or even super-critical) during tasks, then it should increase anti-saccade accuracy relative to sham stimulation.	A decrease in the E/I balance in the FEF following cTBS or an increase in E/I balance following iTBS should make brains more sub-critical or more super-critical, respectively, thus decreasing and increasing the capacity for top-down anti-saccade inhibition, respectively.
Test whether theta-burst stimulation to the frontal eye fields (FEF) alters short term memory relative to sham stimulation.	Increases or decreases in accuracy and trial-to-trial variability in the memory-guided saccade task.	Criticality affords greater dynamic susceptibility to afferent inputs. As such, brains operating closer to criticality will more dynamic instability, undermining performance on tasks dependent on short term memory stability. Theta-burst manipulations which push brains closer to criticality will thus produce greater trial-to-trial variability in accuracy and reaction times on tasks	A decrease in the E/I balance in the FEF following cTBS or an increase in E/I balance following iTBS will make the FEF operate closer to criticality for some people and farther away for others. Operating closer to criticality as a consequence of TMS will thereby cause instability in the short-term

OBJECTIVES	ENDPOINTS	JUSTIFICATION FOR ENDPOINTS	PUTATIVE MECHANISMS OF ACTION
		including memory-guided saccades.	memory representations needed for memory-guided saccades.
Test whether cTBS increases and iTBS decreases subjective cognitive effort associated with task switching between anti- and pro-saccades.	Task switch costs and effort discounting of rewards contingent on the expenditure of cognitive effort following active versus sham FEF stimulation.	Task switching is effortful and subjectively costly, producing effort avoidance. Brains operating closer to criticality have more dynamical flexibility and so should reduce switch costs and subjective effort.	A decrease in the E/I balance in the FEF following cTBS or an increase in E/I balance following iTBS will make the FEF operate closer to criticality for some people and farther away for others. Operating closer to criticality as a consequence of TMS will thereby cause result more dynamical flexibility reducing the energy required to shift neural dynamics between tasks, and thereby produce lower effort costs.
Secondary			
Tertiary/Exploratory			

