## 2 INTRODUCTION

### 2.1 STUDY RATIONALE

The healthy human brain is a complex, dynamical system which is hypothesized to lie near a phase transition at rest – at the boundary between order and chaos. Proximity to this critical point is functionally adaptive as it affords maximal flexibility, dynamic range, and information handling capacity, with implications for cognitive control. Divergence from this critical point has become correlated with diverse forms of psychopathology and neuropathy suggesting that distance from a critical point is both a potential biomarker of disorder and a target for intervention in disordered brains. We have further hypothesized that subjective cognitive effort is a reflection of divergence from criticality induced by engagement with demanding tasks.

A key control parameter determining distance from criticality in a resting brain is hypothesized to be the balance of cortical excitation to inhibition (the “E/I balance”). Transcranial magnetic stimulation is a widely used experimental and clinical tool for neuromodulation and theta-burst stimulation (TBS) protocols are thought to modulate the E/I balance. Here we test whether we can systematically modulate cortical dynamics away from the critical point with continuous theta-burst stimulation (cTBS) or intermittent theta-burst stimulation (iTBS), which are thought to decrease and increase E/I balance, respectively, and which should, thereby, impact on cognitive control and subjective cognitive effort during performance of the control demanding tasks.

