### 9.1 STATISTICAL HYPOTHESES

- Primary Endpoint(s):

We predict that, relative to pre-stimulation rest, continuous theta burst stimulation (cTBS) will result in a reduction of the local balance of cortical excitation to inhibition as reflected in the functional E/I balance in proximity to stimulated targets. Conversely, we predict that intermittent theta burst stimulation (iTBS) will result in an increase of the local balance of cortical excitation to inhibition as reflected in the functional E/I balance in proximity to stimulated targets. We also predict these changes to exceed any effects of sham stimulation, and thus another set of endpoints will compare the functional E/I balance after sham versus either active stimulation protocol.

We also predict that, relative to pre-stimulation rest, cTBS and iTBS protocols that will either reduce or strengthen markers of critical dynamics (including, e.g., long-range temporal correlations) in proximity to stimulation targets. The direction of the effect will depend on how the brain operates at baseline. For example a brain that operates in a more sub-critical (lower E/I balance) regime will show an increase in long-range temporal correlations following iTBS (because it should raise the functional E/I balance).

We also predict that, relative to sham stimulation, cTBS and iTBS will alter oculomotor task performance. Specifically, because criticality makes brains more flexible and susceptible, protocols which make brains operate closer to criticality will cause performance to become more variable and worse on the memory-guided saccade task which depends on stability of short-term memory representations. Also, because criticality increases information transfer capacity between brain regions, protocols which make brains operate closer to criticality will cause performance to become better on the anti-saccade task which depends on robust top-down communication of control signals to override bottom-up reflexive saccades to the target.

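### Long-range temporal correlations at rest: Section 3 predicts a fall under both protocols, Sections 9.1 and 6.1.1 predict a fall or a rise depending on baseline, and the 9.4.2 model can test only a pooled change

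*Protocol*

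**What the plan says.** **One direction, both protocols.** The first primary objective in Section 3 concerns the cortex at rest. Its endpoint cell reads "Diminished markers of critical dynamics including reduced long-range temporal correlations measured by detrended fluctuation analysis". Its mechanism cell explains that "theta burst stimulation should make the brain more sub-critical and super-critical, respectively, thus dampening these" properties, so cTBS and iTBS are both expected to lower them. Section 2.1 points the same way: the study asks whether either protocol can "systematically modulate cortical dynamics away from the critical point".

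**Either direction, depending on baseline.** Section 9.1 also takes rest before stimulation as its reference, and predicts "cTBS and iTBS protocols that will either reduce or strengthen markers of critical dynamics". It says the sign depends on the participant's baseline state, and its example is a sub-critical brain in which long-range temporal correlations rise after iTBS. Section 6.1.1 agrees: each protocol may bring a brain nearer to criticality or take it further away, and nearer means stronger long-range temporal correlations.

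**Analysis.** Section 9.4.2 regresses each outcome on stimulation condition, controlling for sex and age. Section 4.1 adds session order as a covariate, and 9.4.1 adds t-tests of pre against post and of sham against active. Sub-group analyses (9.4.7) are marked not applicable. No rule says how a participant is classed as sub- or super-critical at baseline. Section 9 says that no separate statistical plan will be written, so this text is where the prediction is fixed.

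**The concern.** Long-range temporal correlations are an unsigned marker. They weaken with distance from the critical point on either side, so their expected change depends on where a participant starts. Section 3 fixes the sign as a fall, while 9.1 and 6.1.1 leave it to the baseline. Both describe the resting state, so the difference between rest and task does not separate them.

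Two things are at stake. First, a significant group fall matches Section 3, and a significant group rise can be explained through 9.1, so the reading of this endpoint can be chosen after the result is known. Second, if 9.1 is right and baselines are mixed, the planned test averages changes of opposite sign and may miss a real effect.

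**Working it through.** **1. Predicted change in resting long-range temporal correlations.** The 9.1/6.1.1 column follows from two statements: cTBS lowers and iTBS raises the E/I balance, and the correlations strengthen as the brain nears the critical point. Only the sub-critical/iTBS case is written out in 9.1; the others follow by the same reasoning. All assume that stimulation does not overshoot the critical point.

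| Baseline | Protocol | Section 3, row 1 | Sections 9.1 and 6.1.1 |
|---|---|---|---|
| Sub-critical | cTBS | fall | fall |
| Sub-critical | iTBS | fall | rise |
| Super-critical | cTBS | fall | rise |
| Super-critical | iTBS | fall | fall |

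Two of the four cells conflict. Unless everyone sits at the critical point at baseline, each participant off it has one protocol for which the sections predict opposite signs.

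**2. The plan's own power figure.** Section 9.2 gives 36% for late iTBS (effect size 0.21 in absolute value, n = 60, 0.05). For a two-sided paired t-test with 59 degrees of freedom, the noncentrality is 0.21 × √60 = 1.63 and the power is 35.97%, so the figure reproduces. The claim of more than 95% for cTBS (1.14) also reproduces, at above 99.9%. These effect sizes are for motor evoked potentials and assume one common direction. Section 9.2 gives none for criticality markers.

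**3. What mixed signs do to a pooled test (illustration on assumed inputs).** Let a share q of participants change by −d and the rest by +d, with unit standard deviation within each group.

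- Pooled mean change: −qd + (1 − q)d = d(1 − 2q).
- Standard deviation of the change: √(1 + 4q(1 − q)d²).
- Example, d = 0.84 and q = 0.7: mean = 0.84 × (−0.4) = −0.336; SD = √(1 + 4 × 0.7 × 0.3 × 0.7056) = √1.593 = 1.262; standardised effect = −0.266.

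Power to find a mean fall (n = 60, two-sided 0.05), with d borrowed from the motor evoked potential figures in 9.2:

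| q (share that falls) | d = 0.84 | d = 1.14 |
|---|---|---|
| 1.0 (Section 3) | >99.9% | >99.9% |
| 0.8 | 89% | 97% |
| 0.7 | 53% | 67% |
| 0.6 | 17% | 21% |
| 0.5 | mean change is zero | mean change is zero |

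The documents give neither q nor an effect size for this marker. The table shows only how fast the pooled effect shrinks.

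**4. Can another planned analysis test the 9.1 version?** Section 9.4.2 also plans Pearson correlations between stimulation effects on different measures. These relate one change to another and contain no baseline term. Under 9.1, a drop in functional E/I goes with falling correlations in sub-critical participants and rising ones in super-critical participants, so a correlation pooled over both mixes the signs again.

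**The case against.** **The two texts can be read together.** Section 2.1 starts from a healthy brain resting near the critical point. From there either protocol leads away, and 9.1 adds the individuals who start elsewhere. Section 2.1 is also worded as a test rather than a forecast. This is fair, but the protocol does not say that row 1 is the average case and 9.1 the individual one, and row 1 states its endpoint without condition.

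**Section 9.1 is conditional, not directionless.** This stands: given the baseline state, a sign is predicted and could be refuted. The plan, however, neither defines that state nor uses it in the model.

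**Stronger readings that the documents do not support:**

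- A reader might infer that the whole first objective is irrefutable. It is not. Functional E/I is predicted to fall after cTBS and rise after iTBS (6.1.1, 9.1), and the branching ratio is read as below or above 1.0 in line with the sub- and super-critical shifts in Sections 3 and 4.1. A result against those signs would count against the hypothesis.
- A reader might infer an inflated type I error. A two-sided test at 0.05 has its planned level, and 9.4.1 plans a multiplicity correction. The fault lies in the interpretation, not in the error rate.
- A reader might see the same contradiction in the effort row, where the objective is "Test whether cTBS increases and iTBS decreases subjective cognitive effort associated with task switching between anti- and pro-saccades" while the mechanism cell says that each protocol "will make the FEF operate closer to criticality for some people and farther away for others". Sections 2.2 and 9.1 largely supply the group direction, because demanding tasks put the average brain on the sub-critical side. The row needs only to say so.
- The anti-saccade row has a two-sided endpoint and refers to the task state, so it is not a comparable conflict.

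**Conclusion.** The point holds for long-range temporal correlations at rest. Section 3, supported by the wording of 2.1, predicts a fall under both protocols. Sections 9.1 and 6.1.1 predict a sign that depends on baseline. The signs are opposite for a sub-critical participant given iTBS and, by the same reasoning, for a super-critical participant given cTBS, barring overshoot. The 9.4.2 model cannot test the 9.1 version, and a group change of either sign could be read as support.

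The size of the cancellation depends on the unknown mix of baselines: negligible if nearly all participants move the same way, complete if they split evenly. The power figures are illustrative, since they borrow effect sizes from another outcome. The contradiction itself does not depend on them. The predictions for functional E/I and branching ratio are unaffected.

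**What to change.** State one prediction for long-range temporal correlations at rest and use it in 2.1, 3, 6.1.1, 9.1 and 9.4.2. Either:

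1. **A fall under both protocols.** Remove the baseline-dependent wording for this marker from 9.1 and 6.1.1, and state that a rise counts against the hypothesis. The 9.4.2 model can then stay as it is for this purpose.
2. **A baseline-dependent sign.** Replace the wording in row 1 that allows only a fall, and adjust 2.1. Define baseline regime by pre-stimulation functional E/I relative to 1.0, which 6.1.1 treats as the critical value and which is already to be measured. The correlations themselves cannot serve, because 9.4.2 gives them a range of about 0.5 to 1.0, which does not show the side. Add a condition-by-baseline functional E/I interaction to 9.4.2 as the test of this endpoint. Under 9.1, the active-minus-sham effect should increase with baseline functional E/I for cTBS and decrease with it for iTBS; the opposite slope counts against the hypothesis.

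In the effort row of Section 3, add that the group direction (cTBS up, iTBS down) rests on the average sub-critical state during tasks stated in 9.1.

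The cost is wording in five sections, one extra model term under option 2, and less freedom to interpret an unexpected sign. Section 9.2 offers no basis for the power of the interaction, so that limit should be stated.
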